UP + TAU condition: After randomization, participants randomized to the UP + TAU condition will undergo TAU at ARMS and be offered 16 additional, twice-weekly group UP sessions, also at ARMS (see *Intervention*). Participants in the UP + TAU condition will undergo the same midand post-treatment assessments as the TAU condition, plus the CSQ-8 and a semi-structured interview to collect feedback about the intervention (see *Measures*). The mid-treatment assessment will occur after each participant's 8th UP session OR between 4-6 weeks after randomization, and the post-treatment assessment will occur within two weeks after each participant's 16th UP session. The same risk assessment procedures for mid- and post-treatment assessments used in the TAU condition will also apply to the UP + TAU condition. Should a UP + TAU participant condition have two consecutive unplanned absences from a UP group session, up to three attempts to contact will be made regarding their absence. There will not be a maximum number of missed UP sessions warranting a participant to step out of the 16-session group protocol. After completing the post-treatment assessment, their participation in the study will be complete.

Group UP sessions will take place at the ARMS program at MGH. Study assessment visits (screening/baseline, mid-treatment, and post-treatment) may take place at the ARMS program, the Depression Clinical and Research Program (DCRP), or the Center for Addiction Medicine (CAM) at MGH. Study staff may walk participants between ARMS and the DCRP or CAM as needed.

In sum, the proposed study involves the following points of contact: (1) obtaining informed consent and screening/baseline assessment, (2) mid-treatment assessment involving self-report questionnaires and TLFB, (3) post-treatment assessment involving self-report questionnaires and TLFB (primary endpoint), and (4) 16 twice-weekly group UP sessions for those randomized to the UP + TAU condition.

If participants are unable to complete the clinician-rated measures in-person at their mid- or post-treatment assessments, they will be given the option to complete this portion of the visit via phone call with a study clinician. Should any risk issues arise, the clinician will complete a risk assessment while on the phone with the participant. A licensed clinician will always be on-site for consultation as needed during assessments conducted over the phone.

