If participants are unable to complete the self-reported measures in-person at their screening/baseline, mid-treatment, or post-treatment assessments, they will be e-mailed a link to the self-report battery in Redcap to complete remotely. Study staff will review the completed SRQ assessment in Redcap within 24 (business) hours of submission for report of suicidal thoughts, and within one week to assure their completeness. Should a participant report suicidal thoughts in the past week on the SITBI-SR, a clinical risk assessment (including severity of ideation and presence of plan, intent, and access to means) will be conducted over the phone by a study clinician to ensure participant safety and that the participant remains stable to be treated in an outpatient setting. Additionally, a clinical risk assessment will be conducted over the phone by a study clinician in response to reports of increased NSSI that are deemed clinically

significant. Up to three attempts to contact will be made for this risk assessment before calling a participant's designated emergency contact.

Participants may receive recruitment and scheduling messages, as well as appointment reminders via e-mail or text message over the course of the study, depending on their preferred method of communication. Up to three consecutive (unanswered) contact attempts to the participant will be made for participants in both conditions to schedule mid- and post-treatment assessments. If a participant misses the mid-treatment assessment, but is still responsive to contact attempts, they will still be able to complete the post-treatment assessment. If a participant in either condition is unresponsive to three consecutive unanswered contact attempts within a three-week period at any point within the 10-week study, they will be considered dropped out from the study and no further follow-up will be made; the ARMS clinical team will also be notified.

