The UP was originally designed as a time-limited, CBT protocol to be delivered in 12 to 16 individual outpatient therapy sessions³⁷. Previous studies have demonstrated that the original UP can be successfully modified for administration in other formats (e.g., 12 2-hour weekly outpatient group sessions⁶⁰, 5 one-hour individual inpatient sessions¹⁹). For this study, the UP will be delivered over the course of 16, 1-hour twice-weekly sessions, delivered over an 8-week period, in order to be consistent with the length of existing group treatment session (1 hour) and average group treatment engagement (8 weeks) at ARMS.

Each of the original 8 UP modules (motivation enhancement, functional assessment of emotions, mindful emotion awareness, cognitive flexibility, countering emotion-driven behaviors, interoceptive exposure, emotion exposure, relapse prevention³⁷) will be delivered to a small group of up to 10 participants. See Table 2 for weekly session content. One UP group will be running at any point in time within ARMS, Admission will be partially rolling, such that new study participants can enter the group intervention at any point through UP Week 5 (and then, for example, would attend UP Weeks 1-4 after UP Week 8). If a participant beginning the group treatment during UP Week 5 misses one of the two UP Week 5 sessions, they will undergo an individual "catch-up" session before UP Week 6 in order to ensure that they have received all the UP Week 5 material before proceeding to UP Week 6. Participants will not be permitted to begin the group during UP Weeks 6-8 as these sessions (interoceptive and emotion exposure exercises) are contingent upon learning the emotion management skills presented during UP Weeks 1-5. Should a group of five participants be randomized to the UP + TAU condition during UP Weeks 6-8, they will wait up to attend their first UP group session until UP Week 1 begins again (up to

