Specific Aim 2: Analyses will be intention-to-treat, such that participants will be analyzed as part of their allocated group irrespective how much treatment was received. Continuous variables (OASIS, ODSIS, BSI, CSS, and Craving Scale scores, frequency of NSSI urges and episodes captured by the SITBI, quantity and frequency of substance use, percent days abstinence [PDA]) will be analyzed with generalized mixed effect modeling, which imputes missing values based on maximum likelihood estimates of missing parameters (*Hypotheses 2a, 2b, 2c, 2d, 2e*). Time-by-condition interactions will be analyzed to test the efficacy of the adjunctive intervention. Known confounding variables (e.g., age, gender) will be included as covariates in these analyses. Effect sizes between the two conditions will also be reported. Although we will test for statistical significance, as previously noted, the primary aim of this pilot study is to estimate the intervention's effect size before conducting larger, more adequately powered future studies.

VII. RISKS AND DISCOMFORTS

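### Three unanswered contacts within three weeks end all follow-up, so one silent mid-treatment scheduling round can mean that the post-treatment (primary endpoint) visit is never attempted

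*Protocol*

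**What the plan says.** All of the contact rules are in Section V of the protocol (Study Procedures).

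- **Scheduling.** Up to three consecutive unanswered "contact attempts to the participant will be made for participants in both conditions to schedule mid- and post-treatment assessments".
- **Dropout trigger.** A participant in either arm who is "unresponsive to three consecutive unanswered contact attempts within a three-week period at any point within the 10-week study" falls under the rule that "they will be considered dropped out from the study and no further follow-up will be made". The ARMS clinical team is notified.
- **The only relief.** It covers a participant who misses the mid-treatment visit "but is still responsive to contact attempts, they will still be able to complete the post-treatment assessment".
- **Absence calls, UP + TAU only.** After two consecutive unplanned absences from the group, "up to three attempts to contact will be made regarding their absence".
- **Timing.** In TAU the mid-treatment visit is 4 to 6 weeks and the post-treatment visit 8 to 10 weeks after randomisation. In UP + TAU the mid-treatment visit follows the 8th session or falls in weeks 4 to 6, and the post-treatment visit is within two weeks after the 16th session. Participants randomised to UP + TAU during UP Weeks 6 to 8 may start up to 4 weeks late: "they will wait up to attend their first UP group session until UP Week 1 begins again".

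The summary of contact points in Section V labels the post-treatment assessment the primary endpoint. Section VI (Specific Aim 2) plans an intention-to-treat analysis by mixed model, "which imputes missing values based on maximum likelihood estimates of missing parameters".

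**The concern.** A full unanswered scheduling round is three attempts, and three attempts is also the dropout trigger. Silence at mid-treatment is thus treated as leaving the study, and the visit that carries the primary endpoint may be lost because nobody asks for it. The relief clause does not help, since it requires the participant to be responsive.

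Three things are at stake.

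- **The Aim 2 outcomes at post-treatment.** A likelihood-based mixed model handles missing values well if they are missing at random given the observed data. If silence goes with relapse or distress, that assumption is doubtful, and no analysis plan can recover visits that were never sought.
- **Acceptability in UP + TAU.** The CSQ-8 and the feedback interview are collected only at post-treatment, so satisfaction would be reported by those who stayed reachable.
- **Comparability of the arms.** The text does not say whether the absence calls count toward the three. The words on timing in the trigger allow that they do, which would give UP + TAU an extra route to dropout. The neighbouring sentences concern scheduling contacts, and equally allow that only those count.

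**Working it through.** **Does the rule operate as described?** Attempts per scheduling round: up to 3. Attempts that trigger dropout: 3 consecutive, within 3 weeks. The two coincide whenever a fully unanswered round is completed within three weeks. No other section provides for contact after the trigger; the emergency contact is used only for risk assessment.

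**When does contact close?**

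- TAU, and UP + TAU without a wait: the first mid-treatment attempt falls in weeks 4 to 6 and three attempts take 0 to 3 weeks. Closure is between week 4 + 0 = 4 and week 6 + 3 = 9. Time left to week 10: 10 − 9 = 1 to 10 − 4 = 6 weeks.
- UP + TAU with the longest stated wait and sessions on schedule: the post-treatment visit falls between week 4 + 8 = 12 and week 4 + 8 + 2 = 14. Closure is between week 4 and week 10 (the rule's own limit). Time left to week 14: 4 to 10 weeks.

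**Size.** The protocol states no dropout rate, effect size or SD, so there is no figure to reproduce and every rate below is an assumption. Let *s* be the share silent in the mid-treatment round and *r* the share of those who would answer a later round, both equal across arms. The protocol gives N = 50, randomised in groups of 5 with two groups to UP + TAU for each one to TAU. Ten groups do not divide 2:1, so the nearest splits are 35/15 and 30/20.

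Visits forgone = 50 × *s* × *r*. Half-width in SD units = t(0.975, n₁+n₂−2) × √(1/n₁ + 1/n₂), with the arm sizes multiplied by 1 − *s* under the rule and by 1 − *s*(1 − *r*) with a later round.

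Example with 35/15, *s* = 0.2, *r* = 0.5:

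- Under the rule: n = 28 and 12, 2.024 × 0.3450 = 0.698.
- With a later round: n = 31.5 and 13.5, 2.017 × 0.3253 = 0.656.
- Cost of the rule: 0.042 SD.

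| *s* = 0.2 | *r* = 0.25 | *r* = 0.5 | *r* = 0.75 |
|---|---|---|---|
| Visits forgone | 2.5 | 5 | 7.5 |
| 35/15: 0.698 under the rule, against | 0.676 | 0.656 | 0.638 |
| 30/20: 0.653 under the rule, against | 0.633 | 0.614 | 0.596 |

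The cost is 0.02 to 0.06 SD at *s* = 0.2, 0.009 to 0.027 SD at *s* = 0.1, and 0.037 to 0.104 SD at *s* = 0.3.

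**Bias.** Let *d* be the gap, in SD, between the silent participants' outcomes and what the model predicts for them. The shift in an arm mean that a later round would correct is *s r d* / (1 − *s*(1 − *r*)). With *d* = 0.5 and *r* = 0.5:

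- *s* = 0.2: 0.05 / 0.90 = 0.056
- *s* = 0.1: 0.025 / 0.95 = 0.026
- contrast, 20% against 10% silent: 0.029
- contrast, 20% against 0%: 0.056
- contrast, equal rates: 0

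For 20% against 10%, with *d* from 0.25 to 1.0 and *r* from 0.25 to 0.75, the contrast moves by 0.008 to 0.081 SD.

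**A less cautious model.** If each attempt goes unanswered independently with probability *q*, the post-treatment visit is lost with probability 1 − (1 − *q*³)² under the rule and *q*³ without it. At *q* = 0.4 that is 12.4% against 6.4%. Independence between rounds is the assumption least kind to the rule: if the same people stay silent throughout, it forgoes almost nothing.

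**The case against.** The rule is explicit, worded the same for both arms, and in keeping with the protocol's other contact caps; fixing a limit is legitimate. It is also narrow. One reply breaks the run, attempts spread over more than three weeks do not trigger it, and someone who replies but misses the mid-treatment visit is kept. Staff track ARMS attendance and hand out gift cards for sessions attended, so the people caught may be largely out of reach already and *r* may be low. In TAU, closure can come as late as week 9, inside the post-treatment window. The half-widths compare post-treatment scores only, whereas the planned model also uses baseline and mid-treatment data. The arm asymmetry is uncertain: the protocol sets no maximum on missed UP sessions, and twice-weekly groups might make that arm easier to reach. Dropout from ARMS treatment (Hypothesis 1b) can still be taken from tracked attendance, and Aim 2 is exploratory.

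Most of this stands as a limit on size. It does not remove the point. The text closes contact after one silent round and never reopens it. The sentence on missed sessions does not deal with unanswered contacts. A cap on attempts per round can be kept without ending the search for the endpoint. Contact by the preferred method, the larger payment for the post-treatment visit, the notice to ARMS and the planned comparison of dropouts with completers do not reopen contact either.

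**Conclusion.** The concern holds. Applied as written, the rule can leave the primary endpoint visit unattempted after a single silent mid-treatment round, and the resulting missing data are avoidable and possibly informative. The likely effect is modest: a few hundredths of an SD in precision, and a similar shift in the contrast if the arms differ in silence. Both rest on assumed rates of silence, later response and outcome gap, none of which the protocol supplies. The change is still worth making, because the pilot exists to obtain acceptability data and an effect-size estimate from 50 people. Confidence is medium: the reading of the rule is firm, its practical effect is not known.

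**What to change.** Amend the contact rule in Section V to state that:

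- three unanswered attempts end only the current scheduling round, and the count restarts for each scheduled assessment in both arms;
- calls about UP absences do not count toward it;
- the post-treatment assessment is attempted in every randomised participant who has not withdrawn consent, using the telephone and REDCap options that Section V already provides.

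Removal on clinical grounds is a separate matter and is not addressed here. Section IX also allows removal for severe noncompliance with study procedures, so the amended rule should cross-refer to it.

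The cost is one protocol amendment under the IRB policies named in Section IX, plus one or at most two further rounds of three attempts per unreachable participant by existing staff. At an assumed 20% silent (10 people) that is 10 × 3 = 30 to 10 × 6 = 60 extra attempts over the whole trial.

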TAU condition: After randomization, participants randomized to the TAU condition will undergo usual care at ARMS for the next 8-10 weeks. Usual care at ARMS typically consists of a combination of up to 3 group therapy sessions per week, individual weekly therapy, and/or psychopharmacology appointments as needed. Some ARMS patients are offered and choose to engage in all three treatment modalities (group therapy, individual therapy, and psychopharmacology), whereas others only engage in one treatment modality. No requirements will be placed on TAU participants with regard to TAU dosage and TAU will be consistent with each participant's clinical treatment plan at ARMS; however, TAU attendance (e.g., number of appointments) for all participants will be tracked by study staff. Four to 6 weeks after randomization, TAU participants will complete a mid-treatment assessment, during which they will complete the same self-report questionnaires (plus TLFB and concomitant treatment log with a study clinician) administered at the screening/baseline visit (see *Measures*). Eight to 10 weeks after randomization, they will repeat the same measures for the in-person "post-treatment" assessment. During both the mid- and post-treatment assessments, should a participant report suicidal thoughts in the past week on the SITBI-SR or clinically significant increases in NSSI, a clinical risk assessment (including severity of ideation and presence of plan, intent, and access to means) will be conducted by a study clinician in order to ensure participant safety and that the

participant remains stable to be treated in an outpatient setting. After completing the post-treatment assessment, their study participation will be complete.

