Emotion Regulation Questionnaire (ERQ⁵⁵). The ERQ is a 10-item self-report measure assessing two emotion regulation strategies—cognitive reappraisal and expressive suppression. It will be used at the three assessment points to capture changes in emotion regulation during the study.

Brief Experiential Avoidance Questionnaire (BEAQ⁵⁶): The 15-item BEAQ is a modified, briefer version of the original 62-item Multidimensional Experiential Avoidance Questionnaire (MEAQ), self-report measure of six experiential avoidance domains: behavioral avoidance, distress aversion, procrastination, distraction/suppression, repression/denial, and distress endurance. It will be used at the three assessment time points to capture changes in experiential avoidance.

Overall Anxiety Severity and Impairment Scale (OASIS⁵⁷). This is a 5-item, self-report measure assessing the anxiety-related severity and impairment in the past week. It will be administered at each of the three assessment points to participants in both conditions. Participants in the UP + TAU condition will also complete it at the start of each UP session, per the treatment protocol³⁷.

Overall Depression Severity and Impairment Scale (ODSIS⁵⁸). This 5-item, self-report measure captures severity and impairment of depression in the past week. It will be administered at each of the three assessment points to participants in both conditions. Participants in the UP + TAU condition will also complete it at the start of each UP session, per the treatment protocol³⁷.

Self-Injurious Thoughts and Behaviors Interview-Clinician-Rated Version (SITBI-CR⁵⁰). This clinician-rated measure will be used to capture suicidal thoughts and behaviors and NSSI over lifetime, past year, past month, and past week at the screening/baseline visit.

Self-Injurious Thoughts and Behaviors Interview-Self-Report Version (SITBI-SR⁵⁰). This self-report measure will be used to capture suicidal thoughts and behaviors and NSSI in the past month at the mid-treatment and post-treatment assessments.

Timeline Follow Back (TLFB^{53,54}). The TLFB will be administered as an interview at all three time points in order to determine frequency and quantity of substance use, as well as percent days abstinent, since the last assessment (or at pre-treatment, over the past month). For the TLFB, participants mark the days on which they used a substance and indicate which substance(s) (and how much) they used.

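### The post-treatment TLFB window depends on whether the mid-treatment visit was attended, so the substance-use outcomes in exploratory Hypothesis 2e mix different periods

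*Protocol*

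**What the plan says.** Three statements in the protocol act together.

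- **Window.** The TLFB entry among the measures in section V gives the period for frequency, quantity and "percent days abstinent, since the last assessment (or at pre-treatment, over the past month"). A fixed look-back is stated for pre-treatment only.
- **Missed mid-treatment visit.** Section V, on contact attempts: "If a participant misses the mid-treatment assessment, but is still responsive to contact attempts, they will still be able to complete the post-treatment assessment".
- **Analysis.** Section VI, Specific Aim 2, lists "quantity and frequency of substance use, percent days abstinence [PDA"] among the continuous outcomes for the mixed model. Efficacy is tested by the time-by-condition interaction.

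Visit timing comes from section V. For TAU: "Four to 6 weeks after randomization, TAU participants will complete a mid-treatment assessment", and post-treatment falls 8 to 10 weeks after randomization. In UP + TAU, the mid-treatment visit follows the 8th session or falls at 4 to 6 weeks, counted from randomization. The timing of the last visit in that arm is tied to the sessions: "the post-treatment assessment will occur within two weeks after each participant's 16th UP session". The list of contact points describes the last visit as "post-treatment assessment involving self-report questionnaires and TLFB (primary endpoint").

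Other recall measures in the same section have windows that do not depend on attendance: one week for the BSI, OASIS and ODSIS, and one month for the SITBI-SR at both follow-up visits.

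**The concern.** For a participant who attended mid-treatment, the post-treatment TLFB describes the later part of the study. For one who missed it, the previous assessment is baseline, so the value also takes in early treatment and any days between baseline and randomization. Both values enter the model as the same time point.

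Maximum likelihood deals with the absent mid-treatment value. It does nothing about an observed post-treatment value that measures a different period. No common look-back, per-day scaling or truncation rule is given for this case.

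At stake is the effect estimate for Hypothesis 2e. Section VI says a main purpose of the pilot is to estimate effect sizes for a larger trial, so an outcome whose meaning depends on attendance weakens what is carried forward.

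**Working it through.** The protocol gives no window length to reproduce, so the check is arithmetic on its visit times, followed by an illustration with assumed use rates.

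**Window lengths** (weeks from randomization, baseline taken as week 0)

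Attended window = post − mid. Missed-mid window = post − 0. Ratio = post / (post − mid).

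- Nominal schedule (Table 1, Weeks 4 and 8): attended 8 − 4 = 4; missed 8; ratio 2.0.
- TAU (mid 4–6, post 8–10): attended from 8 − 6 = 2 to 10 − 4 = 6; missed 8 to 10. The lowest ratio is 10/6 = 1.67 and the highest 8/2 = 4.0.
- UP + TAU (wait of 0–4 weeks from the UP treatment description, 8 weeks of sessions, post-treatment 0–2 weeks later): missed 8 to 4 + 8 + 2 = 14. The lowest ratio is 14/(14 − 4) = 1.4 and the highest 8/(8 − 6) = 4.0.
- Section IV randomizes a block only once its last member has completed baseline. The gap is not stated. If it were 2 weeks (assumed), the TAU ratios would become (10 + 2)/6 = 2.0 to (8 + 2)/2 = 5.0.

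**Effect of the window on one participant's score** (28 days in each half; daily use rates assumed)

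| Use, weeks 1–4 then 5–8 | PDA, mid attended | PDA, mid missed | Use-days, attended | Use-days, missed |
|---|---|---|---|---|
| 50%, 50% | 50% | 50% | 14 | 28 |
| 40%, 20% | 80% | 70% | 28 × 0.2 = 5.6 | 28 × 0.4 + 28 × 0.2 = 16.8 |
| 30%, 50% | 50% | 60% | 14 | 22.4 |

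With constant use the raw count doubles and PDA does not move. With falling use a missed visit makes PDA look worse; with rising use it makes PDA look better.

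**Effect on the arm comparison** (40% then 20% in both arms, no true difference)

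Assume 30% of one arm and 10% of the other miss mid-treatment.

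- PDA: (0.30 − 0.10) × (80 − 70) = 2 points.
- Use-days per 28 days: a missed-mid value is 16.8/2 = 8.4, so (0.30 − 0.10) × (8.4 − 5.6) = 0.56.
- Raw use-days, if totals are modelled unscaled: (0.30 − 0.10) × (16.8 − 5.6) = 2.24.
- Equal missing rates and equal trajectories: 0 on every scale.

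**Equal missing rates, different trajectories.** Assume 20% miss in both arms, with use going from 50% to 30% of days in one arm and from 50% to 40% in the other. Late-period PDA is 70 and 60. A missed visit lowers PDA by 10 and 5 points respectively, so the arm means become 70 − 0.20 × 10 = 68 and 60 − 0.20 × 5 = 59. A true difference of 10 points is estimated as 9.

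**Common fixed window.** The ratio is 1.0 for everyone, and the differences created by the window in these examples become zero.

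**The case against.** The strongest reply is that the TLFB entry describes what the interview covers, not how the outcome is scored. Participants mark individual days, so reaching back to the last completed visit leaves no gap, and a common window can be cut from data already collected. A statistical analysis plan, not shown here, may do that. This stands in part: data collection is sound and the problem can be repaired at analysis. But the protocol attaches the variable window to the outcomes themselves, so it states a rule rather than leaving one open. Reading the previous assessment as the previous scheduled visit would remove the problem, but the text does not say so.

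A second reply is that Hypothesis 2e concerns use over the study period, for which a calendar from baseline is appropriate. That would hold for a single summary over the whole study. Section VI instead tests the hypothesis through time-by-condition terms, which need each visit's value to mean the same thing for everyone.

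Third, section V allows clinician-rated measures to be done by phone at mid- and post-treatment. The TLFB is an interview with a study clinician, so this plausibly applies and should make missed mid-treatment TLFBs less common. It does not settle how the remaining ones are scored.

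Stronger readings are tempting but not supported:

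- *The trial's primary endpoint is compromised.* The label is attached to the post-treatment assessment as a whole. Section VI gives the primary aim as feasibility, acceptability and effect-size estimation, and substance use falls under Aim 2, which is exploratory.
- *Hypothesis 2e will show a false arm difference.* The documents give no missed-visit rates or use trajectories by arm, so this remains conditional.
- *Everyone else shares one window.* They do not, as the TAU range of 2 to 6 weeks shows.
- *A longer window by itself worsens every outcome.* This is true of unscaled counts but not of PDA or per-day rates, and the protocol does not say that raw totals are modelled.

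**Conclusion.** The point holds in limited form. Taken literally, the window rule and the missed-visit rule make the post-treatment substance-use value depend on mid-treatment attendance: nominally 8 weeks against 4, with a ratio of about 1.4 to 4 over the allowed visit times before any pre-randomization gap. The upper UP + TAU window assumes the full 4-week wait. The certain consequence is a mixed outcome definition and added noise in the Hypothesis 2e estimate.

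Between-arm bias is possible, not established. In the equal-trajectory illustration it is modest: 2 PDA points, or 0.56 use-days per 28 days. The larger figure of 2.24 use-days requires unscaled counts. All three rest on assumed use rates and assumed missed-visit rates of 30% and 10%. The point is worth correcting because the correction is simple, but it does not threaten the trial's main purpose.

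**What to change.** Keep collecting the day-level calendar back to the last completed assessment. Add to the TLFB entry in section V that mid- and post-treatment quantity, frequency and PDA are scored per day over the same fixed windows for all participants, whether or not mid-treatment was attended. For example, the post-treatment window could be the 28 days before the post-treatment visit. Where mid-treatment was missed, score the earlier post-randomization days on the calendar as the mid-treatment period. Where mid- and post-treatment visits are less than 28 days apart, the days before the mid-treatment visit are already on that visit's calendar; the text should say how days falling in both windows are handled.

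Starting the window at randomization would remove pre-randomization days but would leave the dependence on attendance.

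The cost is a short addition to the measures section and a scoring rule, with no added visits and no longer interview than the current text implies. The downside is that days recovered for a missed mid-treatment visit rest on longer recall, so they should be flagged in the data.
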